13.6 Termination of Study

The Sponsor reserves the right to suspend enrollment or terminate the study at any time for any reason. The Sponsor may suspend enrollment or terminate the study at a specific investigational site for reasons including, but not limited to, inadequate data collection, low participant enrollment rate, achievement of the total enrollment, conditions imposed by the reviewing IRB/EC and/or non-compliance with this protocol or other clinical research requirements. Written notice will be submitted to the Investigator in advance of such termination.

In the event of study suspension or termination, the Sponsor will send a report outlining the circumstances to the IRB/EC, and all Investigators and Regulatory Authorities as

required by regulation. If the study was terminated, resumption would be done according to 21 CFR Part 812.

14.0 ETHICAL AND REGULATORY CONSIDERATIONS

14.1 IRB/EC Approval

Investigators or designees must submit the study protocol, Informed Consent Form (if applicable), and all other locally required documentation to an appropriate IRB/EC and obtain study-specific written approval (favorable opinion) before being allowed to participate in the study. Before commencement of the study, the Investigator or designee must provide the Sponsor with written documentation of such approval. If applicable, the IRB/EC must give written renewal of the original approval at least annually to continue the study. A copy of the written renewal must be provided to the Sponsor.

The IRB/EC will be notified of any amendments to the protocol, as well as possible associated information and consent form changes, where applicable, and written approval (favorable opinion) will be obtained prior to implementation, as applicable.

The Investigator or designee is responsible for fulfilling any conditions of approval imposed by the IRB/EC, such as regular safety reporting, study timing, etc. The Investigator or designee will provide the Sponsor with copies of such reports.

14.2 Informed Consent and Confidentiality

Prior to any study procedure, the Investigator (or designee) must explain to each participant in layman's terms, the nature of the study, its purpose, expected duration, and the risks and benefits of study participation. Also, participant will be informed of uses and disclosures of their medical information for research purposes, and their rights to access information about them. All applicable national privacy laws (e.g., HIPAA requirements in the U.S., General Data Protection Regulation [GDPR] requirements in the EU) will be followed in this study. The participants must be informed of their right to withdraw from the study at any time and for any reason without sanction, penalty, or loss of benefits to which they are otherwise entitled, and that withdrawal from the study will not jeopardize their future medical care. Participants will be informed of their right to new information and/or findings relating to the clinical study, and the process by which this information is made available. After this explanation, given sufficient time to decide whether to participant must voluntarily provide consent in accordance with 21 CFR Parts 50 and 56 and ISO 14155:2020(E). The participant will receive a copy of his/her signed ICF.

14.3 Confidentiality

Participant confidentiality must be strictly held in trust by the Investigator, study staff, and the Sponsor. Participant confidentiality and anonymity will be maintained by removal of identifiers from any data, documentation, or clinical samples submitted to the Sponsor.

Any data collected meeting the definition of protected/confidential health information or personal identifying information will be collected and maintained using the designated authorizations and following privacy procedures as specified in the applicable health authority regulations.

The Sponsor-Monitor, authorized representatives of the sponsor, and/or applicable Health Authorities may inspect all documents and records required to be maintained by the Investigator. The Investigator/Site will permit access to such records.

14.4 Regulatory Status

The PureWickTM System, comprised of the PureWickTM Female External Catheter and the PureWickTM Urine Collection System, is a Class I, 510(k) exempt device currently marketed in the United States and will be evaluated for its approved indication. The investigational device is CE marked and will be studied in a post-market fashion in Europe.

The Sponsor has determined this to be a non-significant risk study. Institutional Review Board (IRB) or Ethics Committee (EC) submission of this study plan along with IRB/EC study approval or waiver is required. The study will comply with the abbreviated IDE requirements under CFR 812.2 (b).

14.5 Statement of Compliance

This clinical investigation will be conducted in compliance with the investigator agreement, protocol and following regulatory requirements:

- 21 CFR 50, 54, 56 and 812;
- 21 CFR 812 (Good Clinical Practice);
- ISO14155:2020 (Good Clinical Practice);
- EU MDR (Council Regulation 2017/745 of 5 April 2017)
- MDCG guidelines
- Ethical principles that have their origin in the Declaration of Helsinki; and
- Applicable sections of the national laws and regulations.

The clinical investigation will not commence at a clinical site until approval (favorable opinion) from the respective IRB/EC has been received. All additional requirements imposed by the IRB/EC(s) will be followed. Involvement of the national competent authorities (e.g. by notification, seeking authorization) will be accomplished as required by national laws and regulations.

16.0 APPENDICES

Appendix 1 : Draize Scale for Skin Irritation

Draize Scale for Skin Irritation

| Score | Erythema (redness) | Edema (swelling) | Bleeding |
|-------|--|---|--|
| 0 | None | None | None |
| 1 | Very slight (barely perceptible) erythema | Very slight (barely perceptible) skin surface rise | Just a visible spot of red |
| 2 | Well-defined erythema | Well-defined skin surface rise (edges of area well-defined by definite raising) | A drop of red blood |
| 3 | Moderate erythema | Moderate skin surface rise | A continuing ooze of red blood |
| 4 | Severe (beet red) or damage to skin (eschar formation) | Severe skin surface rise | Significant bleeding from the sight |

Reference: Draize J.H., Woodward G., Calvery H.O. Method for the study of irritation and toxicity of substances applied topically to the skin and mucous membranes. *J Pharmacol Exp Ther*. 1944; 82: 377-390

Appendix 2: Katz ADL assessment Score

Appendix 3: PureWickTM Female External Catheter Instructions for Use PWFX30 (US)

Appendix 4: PureWickTM Female External Catheter Instructions for Use PWFX30E (EU)

Appendix 5: PureWick[™] Urine Collection System Instructions for Use PW100 & PW 200 (US)

Appendix 6: PureWick[™] Urine Collection System Instructions for Use PW200E (EU)

Appendix 7: Hollister[®] Female Urinary Pouch External Collection Device Instructions for Use

Appendix 8: N-QOL English

Appendix 9: N-QOL French

Appendix 10: PROMIS English

Appendix 11: PROMIS French

Appendix 12 : Participant Comfort Questionnaire PureWick[™] System (Sample)

| Participant Number: | | Visit#: | | | |
|--|--|---|---------------------|---------------------|--|
| Now that you have experienced the use of each device as well as voiding with the device in place, please answer the following questions. | | | | | |
| 1. On a scale of 1 comfortable was the | 1. On a scale of 1 to 5 where 1 is very uncomfortable and 5 is very comfortable, how comfortable was the placement of the PureWick [™] Female External Catheter? | | | | |
| 1 | 2 | 3 | 4 | 5 | |
| Very uncomfortable | Uncomfortable | Neither comfortable nor uncomfortable | Comfortable | Very Comfortable | |
| Comments: | | | | | |
| 2. On a scale of 1 comfortable was the | to 5 where 1 is very ne PureWick [™] Syst | uncomfortable and em during sleep? | 5 is very comfortab | le, how | |
| 1 | 2 | 3 | 4 | 5 | |
| Very | Uncomfortable | Neither | Comfortable | Very | |
| uncomfortable | | comfortable nor uncomfortable | | Comfortable | |
| Comments: | | | | | |
| 3. On a scale of 1 to 5 where 1 is very uncomfortable and 5 is very comfortable, how comfortable was the removal of the PureWick [™] Female External Catheter? | | | | | |
| 1 | 2 | 3 | 4 | 5 | |
| Very uncomfortable | Uncomfortable | Neither comfortable nor uncomfortable | Comfortable | Very Comfortable | |
| Comments: | | | | | |
| | | | | | |

| 4. On a scale of 1 to 5 where 1 is very unlikely and 5 is very likely, how likely would you be to recommend the PureWick [™] System to one of your loved ones? | | | | |
|---|----------|--------------------------------|--------|-------------|
| 1 | 2 | 3 | 4 | 5 |
| Very unlikely | Unlikely | Neither likely nor unlikely | Likely | Very Likely |
| Comments: | | | | |
| | | | | |
| | | | | |
| | | | | |

Appendix 13 : Participant Comfort Questionnaire Hollister® Female Urinary Pouch External Collection Device (Sample)

| Participant Number: | | | Visit#: | | |
|---|--|---|--|-----------------------------|--|
| Now that you have place, please answ | Now that you have experienced the use of each device as well as voiding with the device in place, please answer the following questions. | | | | |
| 1. On a scale of 1 comfortable was th Device? | to 5 where 1 is very ne placement of the | uncomfortable and Hollister® Female | 1 5 is very comfortab Urinary Pouch Exter | ole, how rnal Collection | |
| 1 | 2 | 3 | 4 | 5 | |
| Very uncomfortable | Uncomfortable | Neither comfortable nor uncomfortable | Comfortable | Very Comfortable | |
| Comments: | | | | | |
| 2. On a scale of 1 to 5 where 1 is very uncomfortable and 5 is very comfortable, how comfortable was the Hollister® Female Urinary Pouch External Collection Device during sleep? | | | | | |
| 1 | 2 | 3 | 4 | 5 | |
| Very uncomfortable | Uncomfortable | Neither comfortable nor uncomfortable | Comfortable | Very Comfortable | |

| Comments: | | | | |
|---|-----------------------------|---|---------------------|---------------------|
| | | | | |
| 3. On a scale of 1 | to 5 where 1 is very | uncomfortable and | 5 is very comfortal | ble, how |
| Device? | ne removal of the Ho | ollister® Female Or | inary Pouch Externa | al Collection |
| 1 | 2 | 3 | 4 | 5 |
| Very uncomfortable | Uncomfortable | Neither comfortable nor uncomfortable | Comfortable | Very Comfortable |
| Comments: | | | | |
| 4. On a scale of 1 to 5 where 1 is very unlikely and 5 is very likely, how likely would you be to recommend the Hollister® Female Urinary Pouch External Collection Device to one of your loved ones? | | | | |
| 1 | 2 | 3 | 4 | 5 |
| Very unlikely | Unlikely | Neither likely nor unlikely | Likely | Very Likely |
| Comments: | | | | |
| | | | | |
| | | | | |

Appendix 14 : PureWick[™] System Participant Ease of Use Questionnaire (Sample)

| Participant Number: | | | Visit #: | | |
|--|-----------------------|-----------------------|---------------|-----------|--|
| | | | | | |
| 1. On a scale of 1 to 5 where 1 is very difficult and 5 is very easy, how easy was the set up and placement of the PureWick TM System? | | | | | |
| 1 | 2 | 3 4 5 | | | |
| Very difficult | Somewhat difficult | Average difficulty | Somewhat easy | Very easy | |
| Comments: | | | | | |
| On a scale of 1 to 5 where 1 is very difficult and 5 is very easy, how easy was the removal of the PureWick[™] FEC? | | | | | |
| 1 | 2 | 3 | 4 | 5 | |

| Very difficult | Somewhat difficult | Average difficulty | Somewhat easy | Very easy | | | |
|---|---|-----------------------|-----------------------------|--|--|--|--|
| Comments: | | | | | | | |
| 3. How would y sleep? | 3. How would you describe the dryness experienced with the PureWick [™] System during sleep? | | | | | | |
| 1 | 1 2 3- 4 | | | | | | |
| Never Dry (unacceptable) Sometimes Dry (unacceptable) | | | Usually Dry (acceptable) | Always Dry to mostly always dry (acceptable) | | | |
| Comments: | | | | | | | |

Appendix 15: Hollister® Female Urinary Pouch External Collection Device Participant Ease of use Questionnaire (Sample)

| Participant Number: | | Visit #: | Visit #: | | | |
|--|-----------------------|-----------------------|---------------|-----------|--|--|
| | | | | | | |
| 1. On a scale of 1 to 5 where 1 is very difficult and 5 is very easy, how easy was the placement of the Hollister® Female Urinary Pouch External Collection Device? | | | | | | |
| 1 | 2 | 3 | 4 | 5 | | |
| Very difficult | Somewhat difficult | Average difficulty | Somewhat easy | Very easy | | |
| Comments: | | | | | | |
| On a scale of 1 to 5 where 1 is very difficult and 5 is very easy, how easy was the removal of the Hollister® Female Urinary Pouch External Collection Device? | | | | | | |
| 1 | 2 | 3 | 4 | 5 | | |
| Very difficult | Somewhat difficult | Average difficulty | Somewhat easy | Very easy | | |
| Comments: | | | · | | | |

| 3. How would you describe the dryness experienced with the Hollister® Female Urinary Pouch External Collection Device during sleep? | | | | |
|--|---------------------------------|-----------------------------|--|--|
| 1 | 2 | 3 | 4 | |
| Never Dry (unacceptable) | Sometimes Dry (unacceptable) | Usually Dry (acceptable) | Always Dry to mostly always dry (acceptable) | |
| Comments: | | | | |

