3.0 OBJECTIVES AND ENDPOINTS

| Objectives | Endpoints |
|---|--|
| Primary | |
| To compare efficacy and safety of PureWick TM System and Hollister® Female Urinary Pouch External Collection Device | Efficacy – Daily capture rate via bed pad weights and captured volume. Safety – Daily skin irritation score using the Draize Scale. |
| Secondary | |
| To assess impact of PureWick [™] System and Hollister® Female Urinary Pouch External Collection Device on Nocturnal Incontinence related Quality of Life. | Nocturia Quality of Life (N-QOL) score collected at baseline and every 2 weeks during treatment. PROMIS Sleep Disturbance score collected at baseline and every 7 days during treatment. |
| Tolerability – To assess the tolerance of PureWick TM System and Hollister® Female Urinary Pouch External Collection Device over the expected duration of use | Tolerability – Number of days of actual use of both devices & Discontinuation rate attributed to the device's inconvenience or discomfort |
| To assess participant device preference, comfort, and ease of use of PureWick TM System and Hollister® Female Urinary Pouch External Collection Device To assess participant preference between the PureWick TM System and Hollister® Female Urinary Pouch External Collection Device after study completion | Overall comfort and ease of use scores on a 5-point Likert scale (brief questionnaire) collected at the end of each treatment phase. Overall preference via end of study participant preference survey administered at study completion |
| Tertiary/Exploratory | |
| N/A | N/A |

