7.4 User Preference Questionnaire

Prior to each treatment phase completion, the participant will be asked to complete a short questionnaire on their experience with the PureWickTM System or the Hollister® FUP. The questionnaire is designed to assess the following:

- Comfort with PureWick[™] FEC/PureWick[™] Urine Collection System or the Hollister[®] Female Urinary Pouch External Collection Device
- Ease of use in placing and removing the PureWickTM FEC and the Hollister[®] Female Urinary Pouch External Collection Device

After completing both treatment phases for the study, the participant will complete the preference questions on their experience with the PureWickTM System and the Hollister® FUP. The survey is designed to assess the following:

• The participants preferred device after using both the PureWick[™] FEC/PureWick[™] Urine Collection System and the Hollister® Female Urinary Pouch External Collection Device.

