5.2.3.5 Comfort, Ease of Use and Confidence

Items in the questionnaire will be summarized both as categorical variable (using frequency count and percentage) and as continuous variables (using mean, standard deviation, median, and range) by treatment.

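### Ease-of-use item 1 covers set-up and placement for PureWick but placement alone for Hollister, so the by-device summaries of that item partly reflect the question

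*Protocol*

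**What the plan says.** Participant ease of use is a secondary objective. The endpoint in protocol section 3.0 is "Overall comfort and ease of use scores on a 5-point Likert scale", collected at the end of each treatment phase. Section 7.4 says what the questionnaire is meant to capture: "Ease of use in placing and removing the" PureWick catheter and the Hollister pouch. It does not mention set-up.

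Each device has its own form. In Appendix 14, PureWick item 1 asks "how easy was the set up and placement of the PureWick" System. In Appendix 15, Hollister item 1 asks "how easy was the placement of the Hollister® Female Urinary Pouch External Collection Device". Both items open with the same scale: "On a scale of 1 to 5 where 1 is very difficult and 5 is very easy".

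The analysis is in SAP 5.2.3.5 (matching protocol 10.6.5): "Items in the questionnaire will be summarized both as categorical variable (using frequency count and percentage) and as continuous variables", by treatment. Nothing in either document comments on the difference between the two stems.

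**The concern.** Two columns of item 1 results under one label will be read as the same question asked of two devices. Here they are not. A PureWick respondent rates two tasks on the whole System (suction unit, canister, tubing and catheter). A Hollister respondent rates one task on the pouch.

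The protocol's main protection against bias is the within-subject design, together with standardised questionnaires (section 6.7). Neither helps here. The wording is tied to the device, so it follows the device in both sequences and both phases and stays in any within-woman difference. The item is also not standardised across devices.

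The study is intended to support reimbursement and to inform a later randomised trial (section 2.3). The stakes are a small misreading of one item now, and the same mismatch in the larger trial if the forms are reused.

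**Working it through.** The documents give no figure for this item, so there is nothing to recompute. The check is a side-by-side reading of the forms and the sections that describe them.

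| Item | PureWick form | Hollister form | Same task? |
|---|---|---|---|
| Ease 1 (App. 14 / 15) | Set-up and placement, System | Placement, pouch | No |
| Ease 2 (App. 14 / 15) | Removal, catheter | Removal, pouch | Yes |
| Ease 3 (App. 14 / 15) | Dryness in sleep, four categories | Dryness in sleep, four categories | Yes |
| Comfort 1 (App. 12 / 13) | Placement, catheter | Placement, pouch | Yes |
| Comfort 2 (App. 12 / 13) | Comfort in sleep | Comfort in sleep | Yes |
| Comfort 3 (App. 12 / 13) | Removal, catheter | Removal, pouch | Yes |
| Comfort 4 (App. 12 / 13) | Would recommend | Would recommend | Yes |

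1. **The mismatch is confined to one item.** Ease item 1 is the only one of the seven paired items whose task differs. It is 1 of the 3 items on the ease-of-use form.

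2. **It departs from the stated construct.** Section 7.4 names placing and removing for both devices, and for PureWick names the catheter. Appendix 14 item 1 adds a task (set-up) and widens the object (System instead of catheter). Appendix 15 item 1 matches section 7.4.

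3. **The protocol itself treats set-up and placement as separate.** The benefit statement in section 2.5.1 describes setting up the System and placing the catheter in separate clauses.

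4. **The omission for Hollister is not explained by a lack of set-up.** Section 6.4 lists washing, trimming, optional cutting of the opening and optional barrier paste before the pouch is placed. Section 6.3 says it should be attached to a drainage bag.

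5. **The analysis does not separate the tasks.** SAP 5.2.3.5 reports frequencies and means for each item by treatment. A single rating of two tasks cannot be split afterwards.

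6. **Size and direction.** With true placement ease equal for the two devices, item 1 could still differ by whatever set-up adds to or takes from the PureWick rating. No passage gives a value or a sign for that quantity. Assuming that some share of women shift by one category would only return the assumed share as the mean difference, so no number is offered.

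**The case against.** The strongest reply is that the plan never sets up a formal comparison on this item. The secondary objective is to assess comfort and ease of use, and SAP 5.2.3.5 plans only item-level summaries by treatment. Paired differences are specified elsewhere (capture rate, Draize score, days of use) but not here, and SAP 5.2.1.3 says no formal hypothesis test is planned. This stands, and it limits the weight of the point. What remains is that adjacent columns by treatment invite the comparison, and nothing warns the reader about it.

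Second, set-up is a real property of the PureWick System, so the item does measure something about that device. That is fair: a difference on item 1 would partly reflect the question, not wholly. Some Hollister respondents may also count trimming, cutting or bag attachment as part of placement. That blurs the contrast further and does not restore it.

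Third, a reader might infer that the wording counts against PureWick because it adds a task. The documents do not support that. Section 2.5.1 presents the System as easy to set up; if women find set-up easier than placement, including it could raise the rating.

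Fourth, a reader might add that the dryness item has four categories while the endpoint is described as a 5-point scale, so a combined score would mis-scale it. Neither document defines a combined ease score, the SAP summarises items individually, and the dryness categories are the same on both forms. The endpoint description is loose for that item, but no difference between devices follows.

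**Conclusion.** The point holds as a minor measurement problem. By-treatment summaries of ease-of-use item 1 describe a two-task question for PureWick and a one-task question for Hollister, and part of any difference between them belongs to the wording. Neither size nor direction can be derived, so no bias in favour of or against either device should be claimed.

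The reach is one of three items on a descriptive secondary form. The removal and dryness items and all the comfort items ask matching questions and are unaffected. The primary endpoints are not touched.

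The conclusion assumes that the forms given to participants match the appendices. These are labelled as samples, and the fielded versions are not in the documents.

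**What to change.** 1. Check the fielded forms in both languages against Appendices 14 and 15. If the stems already match, the point falls away.
2. If they do not, use one stem on both forms, changing only the device name: the Appendix 15 pattern, "how easy was the placement of the Hollister", with the PureWick catheter named in its place as in section 7.4. Ask about set-up as a separate item worded identically for both devices, or leave it out. Do this here if forms are still to be completed, and in the future trial in any case.
3. For forms already completed, add a sentence to SAP 5.2.3.5 and a footnote to the item 1 table. Both should state the wording difference and say that no between-device conclusion is drawn from that item.

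The cost is one questionnaire stem, one SAP sentence and one footnote. The downside is that answers to the old and new stems cannot be pooled on item 1, so a change part-way would split an already small sample of about 30. Timing also limits step 2: the SAP is dated 11 September 2024 and the protocol estimated the final report for October 2024. For this study, step 3 is probably the realistic remedy.
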